3 HYPOTHESES, OBJECTIVES, AND ENDPOINTS

There are no hypotheses to be tested in this study.

The following objectives will be evaluated in adults at low-risk of human immunodeficiency virus type 1 (HIV-1) infection.

Primary Objective	Primary Endpoint
To evaluate the safety and tolerability of MK-8527 once monthly (3 mg, 6 mg, and 12 mg) during treatment and through the last follow-up visit.	Adverse events Adverse events leading to discontinuation of study intervention
Secondary Objective	Secondary Endpoint
To characterize the plasma pharmacokinetic profile of MK-8527 once monthly (3 mg, 6 mg, and 12 mg).	MK-8527 AUC _{0-last} and C _{max}
Tertiary/Exploratory Objectives	Tertiary/Exploratory Endpoints
To explore a relationship between intracellular MK-8527-MP, MK-8527-DP, and MK-8527-TP: AUC _{0-last} , C _{max} , C _{trough} , concentrations at common time points	PBMC MK-8527-MP, MK-8527-DP, and MK-8527-TP: AUC _{0-last} , C _{max} , C _{trough} , concentrations at common time points
To characterize the intracellular pharmacokinetic profile of MK-8527-TP in peripheral blood mononuclear cells up to 8 weeks after the last dose of MK-8527 once monthly (3 mg, 6 mg, and 12 mg).	MK-8527-TP AUC _{0-last} , C _{trough} , C _{max} , and t _{1/2}
To explore the relationship between genetic variation and response to study intervention, and mechanisms of disease. Variation across the human genome may be analyzed for association with the pharmacokinetic and safety data collected in this study	Germline genetic variation and association to clinical data collected in this study

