4.2.1.1 Safety Endpoints

The primary safety endpoints are the number of participants experiencing AEs and the number of participants discontinuing study intervention due to AEs. Safety evaluations will include physical examinations (including vital signs) and laboratory tests performed per the SoA (Section 1.3). AEs will be evaluated at each visit and assessed according to the guidelines in Section 8.4. Participants may be asked to return for unscheduled visits in order to perform additional safety monitoring.

Dose-dependent decreases in total lymphocyte and lymphocyte subset counts were observed in clinical studies with ISL, another investigational NRTI agent. The risk of lymphocyte decreases for MK-8527 at the proposed doses is considered low based on available nonclinical and clinical data. To further assess the risk, hematology with lymphocyte subset counts will be monitored, in conjunction with MK-8527 in plasma and MK-8527-TP in PBMC measurements to allow correlation with any dose-related effects.

In this study, criteria for discontinuation of study intervention for confirmed on-treatment decreases of total lymphocyte count <1000 cells/mm 3 or CD4+ T-cell count <500 cells/mm 3 are based on literature that identifies an increased frequency of infections or increased risk of infections when cell counts drop below these levels, whether caused by disease (eg, HIV infection, systemic lupus erythematosus, rheumatoid arthritis) or by disease-modifying drugs [Giovannoni, G., et al 2018] [Spiezia, A. L., et al 2022] [Merayo-Chalico, J., et al 2013] [Subesinghe, S., et al 2020] [Warny, M., et al 2018], and DAIDS criteria (Version 2.1, July 2017) [National Institute of Allergy and Infectious Diseases 2017]. In addition, discontinuation requires a confirmed $\geq 30\%$ decrease from baseline in either total lymphocytes or CD4+ T-cell counts (Table 3) so that participants whose baseline total lymphocyte counts or CD4+ T-cell counts are just above the discontinuation thresholds are

not discontinued for laboratory findings that are within the natural variability of these tests. A $\geq 30\%$ decrease was chosen based on published literature demonstrating that lymphocyte counts vary as much as 25% in healthy adults when measured as frequently as day-to-day and over longer periods of time (every 6 months for many years) [Aziz, N., et al 2019] [Aziz, N., et al 2019a] [Statland, B. E., et al 1978].

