Note: If a participant has a change in HIV-1-associated risk behavior (Appendix 8), he/she may become eligible to receive a medication approved PrEP (eg, FTC/TDF, FTC/TAF, or cabotegravir IM), and discontinuation from study intervention may be indicated. The investigator should discuss any changes in HIV-1-associated risk behavior with the Sponsor's Clinical Director. The decision to continue the participant on study intervention or discontinue the participant with referral to locally available HIV prevention services, including services for approved PrEP, will be determined by agreement between the investigator and the Sponsor.

Note: If a participant requires PEP for potential occupational or non-occupational HIV exposure, the decision to continue the participant on study intervention or discontinue the participant will be determined by agreement between the investigator and the Sponsor.

- The participant has a confirmed positive serum pregnancy test.
- The participant develops a malignancy after randomization.

- The participant has confirmed HIV-1 or HIV-2 infection.

Note: Participants who become infected with HIV-1 or HIV-2 prior to Follow-up Week 8 may have their treatment unblinded.

Note: Participants who become infected with HIV-1 or HIV-2 during the study will stop receiving study intervention and will be referred to local medical providers for HIV care and treatment. No poststudy ART will be provided by the study.

- The participant has an SAE or Grade 4 laboratory AE assessed by the investigator to be related to study intervention AND that is life-threatening or results in prolonged hospitalization.
- A participant must be discontinued from study intervention and managed per Section 8.11.3.1 if any of the criteria in **Table 3** are confirmed. Participants should interrupt QM blinded dosing pending confirmatory testing.

Note: If the investigator believes there is an alternative explanation for the result (eg, COVID-19), consultation between the investigator and Sponsor is required when evaluating the participant for discontinuation from study intervention.

Table 3 Discontinuation Criteria for Specified Decreases in Total Lymphocyte Counts or CD4+ T-cell Counts

Laboratory Test	Criterion ^a	Confirmation ^{b,c}
Total lymphocyte count	A confirmed on-treatment value <1000 cells/mm ³ with a ≥30% decline from baseline	Repeat measurement 1 to 4 weeks later or at the next scheduled study visit, whichever is sooner

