CD4+ T-cell count	A confirmed on-treatment value <500 cells/mm ³ with a ≥30% decline from baseline	Repeat measurement 1 to 4 weeks later or at the next scheduled study visit, whichever is sooner

^a Baseline is defined as the Day 1 value. If a Day 1 value is not available, then the most recent screening value prior to Day 1 should be considered a participant's baseline value.

^b If a measurement meets the specified discontinuation criteria, a consecutive, confirmatory measurement within the specified time frame is required. Confirmatory laboratory measurements can be conducted at the next clinic visit if the next scheduled visit occurs within the interval required for repeat testing.

^c The time frame for confirmation of decreases in total lymphocyte count or CD4+ T-cell count may be extended in the setting of intercurrent illness, immunization, or study intervention dosing interruptions (due to missed study visits). Allow approximately 4 weeks following resolution of illness, immunization, or study intervention dosing interruptions before collecting the confirmation sample to allow for evaluation of a potential other causal effect.

Discontinuation from study intervention is “permanent.” Once a participant is discontinued, he/she shall not be allowed to restart study intervention.

Participants who are discontinued from study intervention prior to the final dose at Week 20, should continue to be monitored. All follow-up visits and procedures, as outlined in the SoA in Section 1.3.1, should be completed.

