8.4.7 Events of Clinical Interest

Selected serious and nonserious AEs are also known as ECIs and must be reported to the Sponsor.

Events of clinical interest for this study include:

1. Potential DILI events defined as an elevated AST or ALT laboratory value that is greater than or equal to 3× the ULN and an elevated total bilirubin laboratory value that is greater than or equal to 2× the ULN and, at the same time, an alkaline phosphatase laboratory value that is less than 2× the ULN, as determined by way of protocol-specified laboratory testing or unscheduled laboratory testing.*

*Note: These criteria are based on available regulatory guidance documents. The purpose of the criteria is to specify a threshold of abnormal hepatic tests that may require an additional evaluation for an underlying etiology. The study-site guidance for assessment and follow-up of these criteria can be found in the Investigator Study File Binder (or equivalent).

2. A lymphocyte count that meets DAIDS criteria for Grade 3 (<500 cells/mm³) or higher grade, as determined by way of protocol-specified laboratory testing or unscheduled laboratory testing at any time during the study.
3. A CD4+ T-cell count that meets DAIDS criteria for Grade 3 (<200 cells/mm³) or higher grade, as determined by way of protocol-specified laboratory testing or unscheduled laboratory testing at any time during the study.

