10.3.2 Definition of AE

AE definition

- An AE is any untoward medical occurrence in a clinical study participant, temporally associated with the use of study intervention, whether or not considered related to the study intervention.
- Note: An AE can therefore be any unfavorable and unintended sign (including an abnormal laboratory finding), symptom, or disease (new or exacerbated) temporally associated with the use of a study intervention.
- Note: For purposes of AE definition, study intervention includes any pharmaceutical product, biological product, vaccine, diagnostic agent, medical device, combination product, or protocol-specified procedure whether investigational or marketed (including placebo, active comparator product, or run-in intervention), manufactured by, licensed by, provided by, or distributed by the Sponsor for human use in this study.

Events meeting the AE definition

- Any abnormal laboratory test results (hematology, clinical chemistry, or urinalysis) or other safety assessments (eg, ECG, radiological scans, vital signs measurements), including those that worsen from baseline, considered clinically significant in the medical and scientific judgment of the investigator.
- Exacerbation of a chronic or intermittent preexisting condition including either an increase in frequency and/or intensity of the condition.
- New conditions detected or diagnosed after study intervention administration even though it may have been present before the start of the study.

- Signs, symptoms, or the clinical sequelae of a suspected drug-drug interaction.
- Signs, symptoms, or the clinical sequelae of a suspected overdose of either study intervention or a concomitant medication.
- For all reports of overdose (whether accidental or intentional) with an associated AE, the AE term should reflect the clinical symptoms or abnormal test result. An overdose without any associated clinical symptoms or abnormal laboratory results is reported using the terminology “accidental or intentional overdose without adverse effect.”
- Any new cancer or progression of existing cancer.

Events NOT meeting the AE definition

- Medical or surgical procedure (eg, endoscopy, appendectomy): the condition that leads to the procedure is the AE.
- Situations in which an untoward medical occurrence did not occur (social and/or convenience admission to a hospital).

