#### **3.5.1.2 Statistical Methods for Safety Analyses**

There are no safety topics of special interest in this study.

Table 1 Analysis Strategy for Safety Parameters

Analysis Part	Safety Endpoint	Descriptive Statistics	95% Between-group CI
Overall Safety Assessment	Any AE	X	X
	Any serious AE	X	X
	Any drug-related AE	X	X
	Any Grade 3 to 4 AE	X	X
	Any serious and drug-related AE	X	X
	Any Grade 3 to 4 and drug-related AE	X	X
	Discontinued study intervention due to AE	X	X
	AE that resulted in death	X	X
	Specific AEs, SOCs, or PDLCs	X	
	Change from baseline results for laboratory values	X	

AE=adverse event; CI=Confidence Interval; PDLC=Pre-Defined Limit of Change; SOC=System Organ Class.

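### The final analysis has no between-group estimate of participants meeting the lymphocyte/CD4+ stopping rule that is independent of whether the investigator recorded an AE

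*Protocol*

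**What the plan says.** **Stopping rule.** Protocol 7.1 states: "A participant must be discontinued from study intervention and managed per Section 8.11.3.1 if any of the criteria in" Table 3 are confirmed. The lymphocyte criterion is "A confirmed on-treatment value <1000 cells/mm ³ with a ≥30% decline from baseline" and the CD4+ criterion is "A confirmed on-treatment value <500 cells/mm ³ with a ≥30% decline from baseline". The rule works on laboratory values and does not require an AE record.

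**AE status of a laboratory result.** Protocol 10.3.2 counts abnormal results as AEs when they are "considered clinically significant in the medical and scientific judgment of the investigator". Protocol 8.3.5 likewise sends clinically relevant changes to the AE page.

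**Events of clinical interest.** Protocol 8.4.7 says: "Selected serious and nonserious AEs are also known as ECIs and must be reported to the Sponsor". The lymphocyte and CD4+ entries are set by the value alone, at below 500 and below 200 cells/mm³.

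**Primary endpoint.** Protocol section 3 lists AEs and "Adverse events leading to discontinuation of study intervention". Protocol 4.2.1.1 expresses the second as "the number of participants discontinuing study intervention due to AEs". Protocol 9.3.1 and SAP 3.3.1 assess it only up to Week 20.

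**Final analysis.** SAP Table 1 gives a 95% between-group CI to eight AE-based rows. Predefined limits of change and laboratory change from baseline are descriptive only. SAP 3.5.1.2 adds: "There are no safety topics of special interest in this study".

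**Interim review.** SAP 3.6 includes a between-group 95% CI for percent change in lymphocyte count. It also counts, by the laboratory rule, the participants who meet Table 3.

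**The concern.** Lymphocyte decline is the class risk that the protocol singles out (2.3 and 4.2.1.1), and SAP 3.8.1 presents power for a between-group lymphocyte difference. Yet participants taken off drug for exactly this reason have no row of their own among the final between-group intervals. Whether they are counted in the AE-discontinuation row depends on a site-level judgement that the plan does not standardise. Two sites with identical laboratory data could contribute differently to the same estimate.

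There is also a timing gap. Protocol 8.11.3.1 keeps monitoring for Table 3 decreases after the last dose. A participant who first meets the rule then has no dosing left to stop, so the AE-discontinuation row cannot count that participant even if an AE is recorded.

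The study is meant to inform the Phase 3 dose (Protocol 2.1 and 4.3), so a final dose-versus-placebo comparison on this risk has a clear use.

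**Working it through.** **1. Where AE status is left to judgement**

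| Measure (cells/mm³) | Table 3 stopping threshold, with ≥30% fall | Event of clinical interest | Range resting on the investigator's call |
|---|---|---|---|
| Lymphocytes | below 1000 | below 500 | 500-999 |
| CD4+ | below 500 | below 200 | 200-499 |

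Nothing in Protocol 7.1, 8.3.5, 8.4.7, 8.11.3.1 or 10.3.2 makes a Table 3 discontinuation in the last column an AE automatically.

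**2. The plan's own power figure**

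SAP 3.8.1 inputs: 100 versus 50, SD 20, difference 10 points, two-sample t-test (two-sided 5% level assumed).
- Noncentrality = 10 / (20 × √(1/100 + 1/50)) = 10 / 3.464 = 2.887, with 148 degrees of freedom and critical t = 1.976.
- Power = 81.8%, which matches the SAP.

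This is power for a comparison at full size, but SAP Table 1 plans no final between-group interval for laboratory change.

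**3. What the interim comparison offers**

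Half of 350 is 175. At 2:2:2:1 that is about 50 per dose group and 25 on placebo.
- SD 20: noncentrality = 10 / (20 × √(1/50 + 1/25)) = 10 / 4.899 = 2.041, power 52%.
- Over SD 15 to 30 the power runs from 77% to 27%.

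This interval compares means and covers lymphocytes only. The Table 3 count at the interim is a 10% threshold per group, with no between-group interval for the proportion. Under a binomial model with 50 in the group, 10% means at least 5 participants. The chance of reaching that is 57% at a true rate of 10% and 89% at 15%. The separate study-wide ad hoc trigger needs 10% × 350 = 35 participants, which is 35% of one dose group if the events are confined to it.

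**4. How far AE calling moves the final row**

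The documents give no rate for meeting Table 3, so the counts are assumed: 10/100 on a dose and 0/50 on placebo meet the rule, and 2/100 versus 1/50 stop for other AEs. The method is the SAP's Miettinen-Nurminen 95% CI. Its limits are the values d at which |p₁ − p₂ − d| / √V(d) = 1.96. V(d) is the variance at the maximum-likelihood estimates restricted to a difference of d, multiplied by N/(N − 1).

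| Of the ten, called AEs | Dose versus placebo, stopped for AE | Difference (points) | 95% CI |
|---|---|---|---|
| All | 12/100 vs 1/50 | 10 | 0.6 to 18.3 |
| Half | 7/100 vs 1/50 | 5 | -4.0 to 12.2 |
| None | 2/100 vs 1/50 | 0 | -8.7 to 5.4 |

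**5. What a laboratory-based row would show**

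This row does not depend on AE calling. With assumed counts on 100 versus 50:
- 5 vs 0: -2.3 to 11.2 points
- 10 vs 0: 2.6 to 17.5
- 10 vs 1: -1.3 to 15.9
- 15 vs 1: 3.4 to 21.7

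The chance that the interval excludes zero is 8% for true rates of 5% versus 1%, 58% for 10% versus 1%, and 90% for 15% versus 1%. The row gives a stable estimate, but it is not sensitive to a small excess.

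**The case against.** A reader might infer that the plan has no between-group estimate on this risk at all, or that the risk could go unnoticed. The documents do not support either reading.

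- SAP 3.6 plans an interim lymphocyte CI against placebo. It also counts Table 3 events by laboratory value, with a group-level 10% criterion, a study-wide 10% trigger and an enrolment pause.
- An unblinded clinical team reviews AEs and laboratory data throughout (Protocol 6.3.3).
- Laboratory change and predefined limits of change are summarised by group (SAP 3.5.1.1 and Table 1), and primary reasons for discontinuation are displayed (SAP 3.5.3).
- The primary endpoint also includes all AEs, and the primary safety assessment covers laboratory results.

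It is equally tempting to say that these discontinuations count only if an investigator calls an AE. That fails below 500 lymphocytes or 200 CD4+, where the event is reportable on the value alone. Nor do the documents suggest that investigators would withhold the call. The none-called line above is a bound, and investigators may well record a confirmed fall that ends dosing as an AE. The direction of any bias is unknown.

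Finally, the study tests no hypotheses, so the choice of rows that carry an interval is partly one of presentation.

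All of this stands, and it limits the point to the final analysis and to the ranges in step 1. It does not close the gap. The interim interval is about half size, compares means and omits CD4+, and the descriptive tables give no interval.

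**Conclusion.** The point holds in limited form. For lymphocytes of 500-999 or CD4+ of 200-499, a mandatory Table 3 discontinuation reaches the AE-discontinuation row only through the investigator's judgement, and the final analysis has no prespecified between-group estimate of Table 3 events that is free of that judgement. With the assumed counts, AE calling alone moves the estimated difference from 10 points to 0 and decides whether the interval excludes zero. The real event rate and the real calling rate are both unknown, so this shows dependence on AE calling and does not predict bias. The change is worth making because the comparison concerns the risk that the protocol singles out and for which the SAP presents power.

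**What to change.** - Add a row to SAP Table 1: confirmed Table 3 lymphocyte or CD4+ decrease, regardless of AE reporting, through last follow-up. Give a Miettinen-Nurminen 95% CI for each dose versus placebo. State explicitly that confirmed decreases after the last dose count in this row, since Table 3 is worded for on-treatment values.
- Add final between-group 95% CIs for percent change from baseline in lymphocyte and CD4+ counts. For lymphocytes this matches the comparison powered in SAP 3.8.1.

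The laboratory-rule status is already needed for the siDMC review, so no new data are required. The cost is a little more analysis and a few more unadjusted intervals. The AE definition and the clinical stopping rule stay as they are.

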10.3.3 Definition of SAE

If an event is not an AE per definition above, then it cannot be an SAE even if serious conditions are met.

An SAE is defined as any untoward medical occurrence that, at any dose:

- a. Results in death
- b. Is life-threatening
 - The term “life-threatening” in the definition of “serious” refers to an event in which the participant was at risk of death at the time of the event. It does not refer to an event, which hypothetically might have caused death, if it were more severe.
- c. Requires inpatient hospitalization or prolongation of existing hospitalization
 - Hospitalization is defined as an inpatient admission, regardless of length of stay, even if the hospitalization is a precautionary measure for continued observation. (Note: Hospitalization for an elective procedure to treat a preexisting condition that has not worsened is not an SAE.) A preexisting condition is a clinical condition that is diagnosed prior to the use of an MSD product and is documented in the participant’s medical history.
- d. Results in persistent or significant disability/incapacity
 - The term disability means a substantial disruption of a person’s ability to conduct normal life functions.

- This definition is not intended to include experiences of relatively minor medical significance such as uncomplicated headache, nausea, vomiting, diarrhea, influenza, and accidental trauma (eg, sprained ankle) that may interfere with or prevent everyday life functions but do not constitute a substantial disruption.
- e. Is a congenital anomaly/birth defect
 - In offspring of participant taking the product regardless of time to diagnosis.
- f. Other important medical events
 - Medical or scientific judgment should be exercised in deciding whether SAE reporting is appropriate in other situations such as important medical events that may not be immediately life-threatening or result in death or hospitalization but may jeopardize the participant or may require medical or surgical intervention to prevent 1 of the other outcomes listed in the above definition. These events should usually be considered serious.
 - Examples of such events include invasive or malignant cancers, intensive treatment in an emergency room or at home for allergic bronchospasm, blood dyscrasias, or convulsions that do not result in hospitalization, or development of drug dependency or drug abuse.

10.3.4 Additional Events Reported

Additional events that require reporting

In addition to the above criteria, AEs meeting either of the below criteria, although not serious per ICH definition, are reportable to the Sponsor.

- Is a cancer.
- Is associated with an overdose.

